9.0 TREATMENT/INTERVENTION PLAN

Patients will receive 3 components of therapy, as described below.

9.1 Intrathecal 131-I-3F8

Treatment will be given via an Ommaya reservoir that will be placed by neurosurgery if not already present. If the patient has a ventriculoperitoneal shunt, and CSF flow study using the shunt tubing has confirmed acceptable CSF flow, the shunt may be used for the administration of 131-I-3F8.

9.1.1 Premedications for 131-I-3F8

The following pre-medication guidelines are strongly suggested, but may be altered based on the clinical judgment of the investigators without being considered a protocol violation.

To start about 2 weeks prior to injection:

Levetiracetam (Keppra): Start at 10-20 mg/kg divided BID about 2 weeks prior to injection, after one week increase by 10 mg/kg. The pills come in 250 and 500 mg strength and no liquid preparation is currently available. For patients unable to tolerate oral tablets, phenytoin may be substituted. Taper of the anti-convulsant is recommended (decrease dose by about 50% 2 weeks post-injection, then discontinue medication 3 days later) rather than abrupt discontinuation.

To start about 5 days prior to injection:

IRB
PB

Amended: 2/26/08

SSKI: 7 drops daily (to begin 5 days pre-injection and to continue for 2 weeks post-injection)

Liothyronine (Cytomel): 25 mcg/day if weight less than 25 kg, 50 mcg/day if weight greater or equal to 25 kg (to begin 5 days pre-injection and to continue for 2 weeks post-injection)

To start 1-2 days prior to injection:

Dexamethasone (for those patients not already on a higher dose of dexamethasone): 0.5 mg po bid if weight less than 15 kg, 1 mg po bid if weight greater than or equal to 15 kg (to begin about 24 hours pre-injection and to be tapered over 1 to 2 weeks)

To be started about 1 to 2 hours before injection:

Hydroxyzine (Vistaril): 1 mg/kg IV, then Q 4 hours x 24 hours post-injection

Acetaminophen (Tylenol): 10 mg/kg po before injection and then Q4 hours x 24 hours post-injection

Lorazepam (Ativan): 0.05 mg/kg IV x 1

Hydromorphone (Dilaudid): 0.015 mg/kg/dose x 1, then PRN

9.1.2 Treatment and dosimetry

Patients will receive an intrathecal dose of 2 mCi of ¹³¹I-3F8 via the Ommaya reservoir. Distribution throughout the thecal sac will be confirmed via whole body imaging at approximately 24 hours post-injection. Patients will have CSF and blood (2 ml/sample) obtained for radioactivity levels at approximately 5, 15, and 30 minutes, and 1, 2, 4, 18, and 44 hours post-injection. Pharmacokinetic data obtained from whole body and SPECT imaging will be used in conjunction with direct counting of CSF and blood samples in a well scintillation counter, and combined with MRI anatomical imaging to estimate the absorbed dose to brain, spinal column, blood and visible tumor nodules.

About 1 week after the initial dose, patients will receive a therapeutic dose of 10 mCi. They will have the same CSF and blood monitoring specified in the previous paragraph, but will not have the SPECT imaging.

Patients will be hospitalized overnight for supportive care after each of the 2 ¹³¹I-3F8 injections.

9.2 External beam radiation therapy

IRB
PB

Amended: 2/26/08

Memorial Sloan-Kettering Cancer Center
IRB Protocol

IRB#: 02-088A(5)

Dose: A dose of 1800 cGy will be delivered to the craniospinal axis using external beam photons. The posterior fossa tumor bed boost will be treated to a total dose of 5400 cGy (1800 cGy craniospinal + 3600 cGy focal). The whole brain dose is calculated at midplane while the spine dose is calculated at the average anterior cord depth. The IMRT boost will be prescribed to the isodose line that includes at least 95% of the planning target volume (PTV).

Radiation should begin as soon as possible after the patient has recovered from surgery and intrathecal 131-I-3F8. Treatment will be given according to standard fractionation at 180 cGy per day, 5 days per week. All fields shall be treated daily. Days missed due to holidays or for other unavoidable reasons are acceptable but should be kept to a minimum. Holding radiation treatments is allowed at the discretion of the radiation oncologist, but interruptions in radiation therapy should be avoided whenever possible. There are no minimum blood count requirements for radiation therapy and radiation therapy may be given even if chemotherapy is held.

Treatment volume: Radiation will be delivered to the entire craniospinal axis with an inferior border 1 to 2 cm below the thecal sack. Care will be taken to include the cribriform plate while shielding the lenses of the eyes. The clinical target volume (CTV) for the boost to the posterior fossa tumor bed will include the postoperative cavity and any residual disease plus a 1 cm margin in all dimensions. The only exception is that the CTV should not extend into bones (skull base, calvarium, vertebral bodies) and thus the margin may be less than 1 cm in these regions. The PTV is defined as the CTV plus a 0.5 cm margin in all dimensions. The PTV may extend into bones. The entire posterior fossa is NOT intended for treatment in the boost field.

Technique: Patients will receive craniospinal radiation using standard techniques. They will be simulated in the prone position using immobilization casts as well as anesthesia when necessary. A treatment planning CT scan will be performed and images will be fused with a diagnostic MRI scan for better definition of anatomy. The brain will be treated with lateral or lateral oblique fields (depending upon the technique chosen for lens sparing) matched to posterior spine field(s). Appropriate gantry and collimator angles will be calculated to prevent overlapping fields. There will not be a gap between the cranial and spine fields but the match line will be shifted 1 cm half way through treatment, at 900 cGy.

Intensity modulated radiation therapy will be used for focal treatment of the tumor bed boost. The number of fields and orientation of beams will be determined on an individual basis. The general goals of the optimization algorithm are to maximize coverage of the target volume (PTV as defined above) while minimizing heterogeneity within the target and sparing the cochlea to the extent possible. The maximum dose to any point in the brainstem must not exceed 6000 cGy and the maximum dose to any point in the cord must not exceed 5000 cGy in the composite plan (including the craniospinal portion of

IRB
PB

Amended: 2/26/08

Memorial Sloan-Kettering Cancer Center
IRB Protocol

IRB#: 02-088A(5)

treatment). Dose to the hypothalamic-pituitary axis should also be constrained as much as possible. The parotid glands and oral cavity should be contoured and the cumulative mean dose to each of these structures should not exceed 2600 cGy.

All fields will be treated using 6MV photons. Initial and weekly portal films will be taken to ensure correct positioning.

Evaluation on treatment: Patients will be evaluated by a radiation oncologist at least once per week. Complete blood counts will be drawn about weekly.

9.3 Chemotherapy

Starting at about the onset of external beam RT, patients will receive 8 weekly doses of vincristine (1.5 mg/m²/dose, maximum 2 mg).

Starting about 6 weeks after completion of the RT (about 4 weeks after the 8th dose of vincristine noted above), we will start 8 planned cycles of vincristine, cisplatin, and lomustine chemotherapy. Each cycle consists of:

Vincristine (1.5 mg/m²/dose, maximum 2 mg) IV push on days 0, 7, & 14.

Cisplatin (75 mg/m²/dose) IV over about 6 hours on day 0 with mannitol and hydration. A sample order set is included as an appendix.

Lomustine (75 mg/m²/dose) po on day 0. Because the capsules only are available in 10, 40, and 100 mg doses, the actual dose of lomustine will be rounded off to the closest possible dose.

Cycles are intended to be repeated about every 6 weeks depending on the ANC and platelet count (see below). The post-RT chemotherapy may be given at another center if more convenient for the patient as long as adequate documentation is sent to the MSKCC PI in a timely fashion.

9.4 Chemotherapy dose modification rules:

Hematopoietic toxicity: If the ANC is < 750 or platelet count < 75,000, a cycle should not be started. If the ANC is ≥ 750, but < 1000, or the platelet count is ≥ 75,000 but < 100,000, the cycle may start, but the lomustine dose will be reduced by 50%.

Neurotoxicity: For vincristine neurotoxicity grade 3 or 4 and/or for vincristine neuropathy: motor grade 2 to 4: hold vincristine. When toxicity resolves to less than grade 3 (less than grade 2 for vincristine neuropathy: motor), vincristine may be restarted at 50% dose (0.75 mg/m²). If the neurotoxicity completely resolves, increase to full dosage may be considered.

IRB
PB

Amended: 2/26/08

Hepatotoxicity: If total bilirubin is > 1.9 mg/dl, do not administer vincristine dose. If total bilirubin is 1.5 to 1.9 mg/dl, administer vincristine at 1 mg/m^2 (1.5 mg maximum).

Nephrotoxicity: If the creatinine clearance or GFR are > 60 ml/minute/1.73 m², administer the full dose. If the creatinine clearance or GFR are 30-60 ml/minute/1.73 m², administer 50% of the dose (37.5 mg/m^2). If the creatinine clearance or GFR are < 30 ml/minute/1.73 m², do not administer cisplatin.

Ototoxicity: For a decrease in auditory acuity of (1) ≥ 30 decibels at 4000 to 8000 Hz or (2) ≥ 20 decibels at 500 to 3000 Hz or (3) grade 3 ototoxicity (subjective loss correctable with hearing aid), a 50% reduction in cisplatin dosage will be made. For grade 4 ototoxicity (deafness not correctable), cisplatin will be discontinued unless follow-up audiogram shows an improvement in hearing function.

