6.0 CRITERIA FOR PATIENT/SUBJECT ELIGIBILITY

6.1 PATIENT/SUBJECT INCLUSION CRITERIA

- Patients must have histologic proof of medulloblastoma reviewed by the Department of Pathology at the Memorial Sloan-Kettering Cancer Center.
- Patients must begin study prescribed therapy within 42 days of neurosurgical resection of the tumor
- Age \geq 3-years-old.
- Post-operative head MRI must confirm $\leq 1.5 \text{ cm}^2$ of residual tumor is present.
- Head and spine MRI and lumbar CSF cytology must not show any definitive evidence of leptomeningeal dissemination (Chang stage M-0).
- Examinations evaluating extra-neural sites will not be mandated, but any performed for clinical indications must be free of metastatic disease.
- No prior RT or chemotherapy for the medulloblastoma is permitted.
- Patients must have adequate CSF flow (defined as lack of compartmentalization) on an 111-Indium DTPA flow study.
- Patients must have adequate organ function as defined by:
 - Hepatic: total bilirubin $< 2.0 \text{ mg/dl}$, AST $< 3 \times$ the upper limit of normal.
 - Renal: Calculated creatinine clearance or nuclear GFR $\geq 70 \text{ ml/min/1.73 m}^2$.
- The patient, or for minors, a parent or legal guardian, must give informed written consent indicating they are aware of the investigational nature of this study.

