17.0 PROTECTION OF HUMAN SUBJECTS

Most patients on this study will be children, adolescents, and young adults, due to the nature of this tumor type. Patients of both sexes and all ethnic backgrounds are eligible for the study. Participation will be voluntary. Potential benefits include comparable event-free survival with hypothesized decreased risk of long-term side effects (neuropsychological, neuroendocrine, audiometric, growth). Alternatives include external beam radiation therapy alone (3600 cGy craniospinal with posterior fossa boost) or reduced-dose radiation therapy (2340 craniospinal with posterior fossa boost) with the same chemotherapy that will be prescribed in this study.

Patients are responsible for all costs of their care including (but not limited to) physician visits, hospitalizations, medications (except for the 3F8 antibody), MRI scans, and laboratory work (except for dosimetry studies).

Patient confidentiality will be protected, but records may be reviewed by appropriate staff of the Memorial Sloan-Kettering Cancer Center or the Food and Drug Administration (FDA).

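### The vincristine restart dose after neurotoxicity has no mg maximum, so above 1.33 m² its printed rate gives more than the 50% it is labelled as

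*Combined protocol and SAP*

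**What the plan says.** Section 9.3 gives the full dose with its cap twice. During radiation, "patients will receive 8 weekly doses of vincristine (1.5 mg/m²/dose, maximum 2 mg"). In each of the eight later cycles, "Vincristine (1.5 mg/m²/dose, maximum 2 mg) IV push on days 0, 7, & 14".

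Section 9.4 covers dose modification. Under Neurotoxicity, vincristine is held for grade 3 or 4 neurotoxicity or grade 2 to 4 motor neuropathy. Once the toxicity falls below the triggering grade, "vincristine may be restarted at 50% dose (0.75 mg/m²"). No mg maximum follows.

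Two other rules in Section 9.4 are useful comparisons:

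- Hepatotoxicity, also for vincristine: "administer vincristine at 1 mg/m^2 (1.5 mg maximum"). A reduced rate is printed with a reduced maximum.
- Nephrotoxicity, for cisplatin: "administer 50% of the dose (37.5 mg/m^2"). This has the same percentage-plus-rate format, but cisplatin has no maximum in Section 9.3.

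On who may be enrolled, Section 6.1 sets only a lower age limit ("Age \geq 3-years-old"), and Section 17.0 states "Most patients on this study will be children, adolescents, and young adults".

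**The concern.** The restart dose is written in two forms, a percentage and a mg/m² rate. They are equivalent only while the full dose is uncapped. Once a patient is large enough for the 2 mg cap to apply, half the dose is fixed at 1 mg, but the printed rate goes on rising with body surface area. The text does not say which form governs.

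The rule applies to patients who have just had significant vincristine neurotoxicity, and restart is allowed before that toxicity has fully resolved. A prescriber who uses the percentage halves the dose; one who uses the printed rate does not, for a patient above the cap threshold. The plan has 8 weekly doses plus 3 in each of 8 cycles (8 + 3 × 8 = 32), so a restarted patient could receive the higher dose repeatedly. Section 9.3 also allows post-radiation chemotherapy at another center, where the prescriber depends on the written rule.

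**Working it through.** **Inputs.** Full dose 1.5 mg/m², maximum 2 mg (Section 9.3). Restart at 50%, printed as 0.75 mg/m² with no maximum (Section 9.4, Neurotoxicity). Cisplatin 75 mg/m² with no maximum (Section 9.3), reduced to 37.5 mg/m² (Section 9.4, Nephrotoxicity). The documents give no body surface areas (BSA), so those below are assumptions that span a range.

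**The plan's own figure.** 0.5 × 1.5 = 0.75 mg/m². The printed rate is correct as half the full rate.

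**Where the cap binds.** 1.5 × BSA = 2 gives BSA = 2/1.5 = 1.33 m².

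**The two forms of the restart dose.**

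- Percentage form: 0.5 × min(1.5 × BSA, 2)
- Printed rate: 0.75 × BSA

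| BSA (m²) | Full dose (mg) | Percentage form (mg) | Printed rate (mg) | Printed rate as share of full dose | Excess (mg) |
|---|---|---|---|---|---|
| 1.0 | 1.50 | 0.75 | 0.75 | 50% | 0 |
| 1.33 | 2.00 | 1.00 | 1.00 | 50% | 0 |
| 1.4 | 2.00 | 1.00 | 1.05 | 52.5% | 0.05 |
| 1.5 | 2.00 | 1.00 | 1.125 | 56.25% | 0.125 |
| 1.8 | 2.00 | 1.00 | 1.35 | 67.5% | 0.35 |
| 2.0 | 2.00 | 1.00 | 1.50 | 75% | 0.50 |

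**Does carrying over the 2 mg cap help?** No. The printed rate reaches 2 mg only at 2/0.75 = 2.67 m², so that cap leaves every row of the table unchanged.

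**Why the same format works for cisplatin.** 37.5/75 = 50% at every body size, because no maximum applies. Of the three chemotherapy drugs, only vincristine is capped, so the format fails only there.

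**Comparison with the hepatotoxicity rule.** That dose is min(1 × BSA, 1.5) mg. At 2.0 m² it is 1.5 mg. The printed neurotoxicity rate at 2.0 m² is also 0.75 × 2.0 = 1.5 mg. A reduction labelled 50% then gives no less drug than the hepatotoxicity rule, whose rate is cut only to 1/1.5 = 67%.

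**Check of the correction.** With a 1 mg maximum the restart dose is min(0.75 × BSA, 1). Since 0.5 × min(1.5 × BSA, 2) = min(0.75 × BSA, 1), the two forms are identical at every body size. A numerical check from 0.3 to 3.0 m² gave a largest difference of 0.

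**The case against.** The strongest reply is that the sentence already gives the intended dose. The instruction is to restart at half dose, and the mg/m² figure in brackets only explains it. The following sentence speaks of returning to full dosage, which Section 9.3 defines with the 2 mg cap. For a patient who had been receiving 2 mg, half is plainly 1 mg. The higher dose arises only if the prescriber sets the percentage aside, calculates from the bracket and does not compare the result with the previous dose. On this view nothing has been miscalculated, and the point is one of wording.

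Much of this stands. The 0.75 figure is a correct halving of the rate, the percentage reading is a natural one, and the text does not require an overdose. But chemotherapy is commonly ordered by rate and body size. A printed rate that contradicts its own percentage for eligible patients is more than a missing detail.

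A second objection is that the hepatotoxicity rule is weak support, because it cuts the rate to 67% but the maximum only to 75% (1.5/2). That is fair. The rule shows that a reduced vincristine dose can carry its own printed maximum, but not that 1 mg is the right value here. The 1 mg figure rests on the word 50% applied to the 2 mg cap.

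Third, the reach is small. The patient must exceed 1.33 m², have qualifying toxicity, improve, be restarted at the clinician's discretion and be dosed from the bracket. From 1.4 to 1.5 m² the excess is only 0.05 to 0.125 mg, and up to 2.0 m² the printed rate still cuts the capped dose by at least 25%. All of this stands and limits the weight of the point.

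Finally, the content of Appendix A, the model Day 0 order sheet, is not in the text available and could not be checked for a cap. Its title covers Day 0 orders, whereas vincristine is also given on days 7 and 14 and weekly during radiation.

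**Conclusion.** The concern holds. As written, the neurotoxicity restart rule has two values for any patient above 1.33 m². The printed rate exceeds half the capped dose by 0.125 mg at 1.5 m², 0.35 mg at 1.8 m² and 0.50 mg at 2.0 m². No section of the available text settles which form governs. Patients of that size can be enrolled, since there is no upper age limit and adolescents and young adults are expected.

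This should be corrected as a matter of dosing safety, with narrow reach. The conclusion assumes that 50% was meant to apply to the dose actually given, including its cap. The body sizes are illustrative. Without body-size data or a neurotoxicity rate, the number affected cannot be estimated. Nothing in the sample size, stopping rule or planned analysis depends on it.

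**What to change.** In the Neurotoxicity paragraph of Section 9.4, extend the parenthesis after the 50% restart dose so that it reads: 0.75 mg/m², maximum 1 mg. If Appendix A or any local order template covers reduced vincristine doses, give the same maximum there.

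The cost is three words in one sentence, made by amendment. No procedures, patients or analyses are added.

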9.5 Supportive care guidelines

Clinical judgment may be used to alter the following guidelines without being a protocol violation.

Patients should receive PCP prophylaxis.

Filgrastim (G-CSF) is allowed to be used according to clinical judgment.

10.0 EVALUATION DURING TREATMENT/INTERVENTION

A tabular summary of the timing of the mandated observations is included as an appendix to the protocol.

Dosimetry studies during phase 1 of the protocol (see section 9.1).

CBC will be obtained about weekly during external beam radiation therapy.

CBC, total bilirubin, AST, creatinine clearance or GFR, and audiograms will be obtained at baseline and prior to each cycle of cisplatin-containing chemotherapy.

Serum for anti-idiotypic testing (order as Research test: 1 red top tube to be sent to [name] laboratory, Z-1431) will be obtained about every 6 months.

Neuropsychological battery will be performed at "baseline", and at about 1 year and 4 years post-completion of treatment. The "baseline" testing may be performed up to 4 months post-completion of external beam radiation therapy.

The tests in the assessment battery are presented in Table 1 below for parents and children by age and by functional domain assessed. The attending neuropsychologist may

**Memorial Sloan-Kettering Cancer Center
IRB Protocol**

IRB#: 02-088A(5)

make necessary modifications to the battery as indicated for an individual patient's special circumstances without it being considered a protocol violation.

**IRB
PB**

Amended: 2/26/08

Table 1. Neuropsychological and Behavioral Battery

Test	Child's Age				
	> 3 & ≤ 4 yrs	>4 & ≤ 6 yrs	> 6 & ≤ 12 yrs	> 12 & ≤ 16 yrs	> 16 yrs
Children					
Intelligence					
WPPSI-III (Vocabulary, Block Design) (15 min)	X	X			
WISC-IV (Vocabulary, Block Design) (15 min)			X	X	
WAIS-III (Vocabulary, Block Design) (15 min)					X
Processing Speed/Attention					
WPPSI-III (Symbol Search, Coding) (10 min)	X	X			
WISC-IV (Symbol Search, Coding) (10 min)			X	X	
WAIS-III (Symbol Search, Coding) (10 min)					X
Memory					
NEPSY (Story Memory) (5 min)	X (3-5 yrs)				
CMS (15 min)		X (≥ 5 yrs)			
CVLT-C (15 min)		X (≥ 5 yrs)			
WISC-IV (Digit Span) (5 min)			X	X	
WAIS-III (Digit Span) (5 min)					X
WMS-III and CVLT-II (20 min)					X
Parents					
Attention and Behavior/Social/Emotional Function					
BASC-II (20 min)	X				
Executive Function					
BRIEF (5 min)	X	X	X	X	X
Quality of Life					
PedsQL 4.0 (Generic Version)	X	X	X	X	X

Index of Test Abbreviations

WPPSI-III	Wechsler Preschool and Primary Scale of Intelligence – 3 rd Edition
WISC-IV	Wechsler Intelligence Scales for Children – 4 th Edition
WAIS-III	Wechsler Adult Intelligence Scales – 3 rd Edition
NEPSY	NEPSY: A Developmental Neuropsychological Assessment
CMS	Children's Memory Scale
CVLT-C	California Verbal Learning Test – Children's Version
WMS-III	Wechsler Memory Scale – 3 rd Edition
CVLT-II	California Verbal Learning Test – 2 nd Edition
BASC-II	Behavior Assessment System for Children – 2 nd Edition
BRIEF	Behavior Rating Inventory of Executive Function Scales
PedsQL 4.0	Pediatric Quality of Life Inventory Version 4

Neuropsychological Battery

As indicated in Table 1 above, the tests that are administered depend on the child's age at the time of the assessment. Procedural information for the tests in the neuropsychological and behavioral battery is provided by age group in Appendix II. General information about each of the measures in the Neuropsychological and Behavioral Battery is provided below.

Wechsler Preschool and Primary Scale of Intelligence – 3rd Edition (WPPSI-III)

The WPPSI-III is a test for assessment of intellectual function in individuals greater than 2 years of age but less than 7 years of age. Four subtests from this measure will be used: 1. Vocabulary will be utilized to assess verbal intellectual function; 2. Block Design will be utilized to assess nonverbal intellectual function; 3. Symbol Search and 4. Coding will be used to assess processing speed. Reliability for this measure has been reported to be between 0.83 and 0.95. Criterion and discriminant validity have been established for this measure.

Wechsler Intelligence Scales for Children – 4th Edition (WISC-IV)

The WISC-IV is a test for assessment of intellectual function in individuals 7-16 years of age. Five subtests from this measure will be used: 1. Vocabulary will be utilized to assess verbal intellectual function; 2. Block Design will be utilized to assess nonverbal intellectual function; 3. Symbol Search and 4. Coding will be used to assess processing speed; and 5. Digit Span will be used to assess short-term memory. Reliability has been reported between 0.79 and 0.97 for this measure. Construct validity has been established for this measure.

Wechsler Adult Intelligence Scales – 3rd Edition (WAIS-III)

The WAIS-III is a test for assessment of intellectual function in individuals greater than 16 years of age. Five subtests from this measure will be used: 1. Vocabulary will be utilized to assess verbal intellectual function; 2. Block Design will be utilized to assess nonverbal intellectual function; 3. Symbol Search and 4. Coding will be used to assess processing speed; and 5. Digit Span will be used to assess short-term memory. Very good reliability as well as concurrent and criterion validity have been established for this measure.

NEPSY: A Developmental Neuropsychological Assessment

The NEPSY is a test for assessment of a wide range of children's neuropsychological function. One subtest, Story Memory, will be utilized for assessing narrative memory in children 3 to 5 years of age. Reliability of this measure has been reported to be between 0.77 and 0.85. Validity has also been established for this measure.

Children's Memory Scale (CMS)

The CMS is a test to assess verbal and visual memory in individuals 5-16 years of age. The following subtests will be utilized: Story Memory, Story Memory Recall, Faces, Faces Recall, Dot Location, and Dot Location Recall. Reliability and validity have been established for this measure.

California Verbal Learning Test – Child (CVLT-C) or Adult 2nd Edition (CVLT-II)

The CVLT-C and CVLT-II involve verbally presenting a list learning task over the course of 5 trials. The test measures multiple aspects of how verbal learning occurs, or fails to occur, as well as the amount of verbal material learned. The CVLT-C is for individuals 5-16 years of age while the CVLT-II is for individuals older than 16 years of age. Test-retest reliability of this measure has been reported to be between 0.80 and 0.84.

Wechsler Memory Scale – 3rd Edition (WMS-III)

The WMS-III is a test to assess verbal and visual memory in individuals greater than 16 years of age. The following subtests will be utilized: Logical Memory I, Logical Memory II, Faces I, Faces II, and Spatial Span. Internal consistency reliability has been reported to be above 0.70 for this measure. Construct, convergent, and discriminant validity have been established for this measure.

Behavior Assessment System for Children – 2nd Edition (BASC-II)

The BASC-II describes the behaviors, thoughts, and emotions of children and adolescents. The parent rating scale will be utilized for individuals older than 2 years of age. The questionnaire yields composite and scale scores in the domains of externalizing, internalizing, school, and other problems as well as adaptive skills and behavioral symptoms. Internal consistency reliability has been reported to be between 0.80 and 0.95, test-retest reliability between 0.72 to 0.92, and interrater reliability between 0.53 and 0.86. Content and construct validity have been established for this measure.

Behavior Rating Inventory of Executive Function Scales (BRIEF)

The 86-item parent-report version of the BRIEF will be used to assess executive function in individuals 6 years of age and older. This pertains to the following functional areas: inhibition and shifting of attention, emotional control, initiation, working memory, planning, organization and self-monitoring. Internal consistency of the BRIEF has been reported from 0.80 to 0.98 and test-retest reliability has been reported between 0.76 and 0.85. The preschool version of the questionnaire will be utilized for individuals younger

than 6 years of age. Construct, content, convergent, and discriminant validity have also been established for this measure.

Pediatric Quality of Life Inventory Version 4 (PedsQL 4.0)

The PedsQL 4.0 is a modular approach to measuring health-related quality of life in healthy children and adolescents as well as in those with acute and chronic health conditions. The Generic Version consists of 23 items, with parent-report for ages 2-4, 5-7, 8-12, and 13-18. The questionnaire yields domain scores for Physical, Emotional, Social, and School Functioning as well as summary scores for Total, Physical Health, and Psychosocial Health. Reliability and validity have been established for this measure.

Neuroendocrine assessment performed at baseline will include standing and sitting height, Tanner staging of puberty, free thyroxine, TSH, and bone age x-ray. For patients > 12-years-old or who have \geq Tanner 2 puberty, LH/FSH, and testosterone or estradiol will be assessed. Follow-up examinations will be performed until 5 years post-diagnosis and will consist of standing and sitting height, Tanner staging, free thyroxine, and TSH every 6 months. Growth hormone stimulation testing will be performed if yearly growth velocity post-treatment is < 4cm per year or at 2 years post-completion of all therapy, whichever occurs first. Bone age x-ray, and LH/FSH, and testosterone or estradiol for patients > 12 years or who have \geq Tanner 2 puberty, will be performed annually.

Assessment of tumor status via brain MRI will be performed about 4 weeks after completing RT (pre-cycle 1 chemotherapy), then about every 3 months while on therapy (prior to cycles 3, 5, and 7). After completion of therapy, brain MRI scans will be performed about every 3 months for 1 year, then every 6 months for 2 years, then every 12 months for 1 year. Total spine MRI scans will be performed at about 1 year, 2 years, and 3 years post-completion of therapy. Subsequent scans will be performed at the clinician's discretion and are not mandated by this protocol, but brain MRI scans are recommended to be done about annually.

Mandated evaluations including lab work, audiograms, and MRI scans may be performed at other (non-MSKCC) centers if deemed clinically indicated by an investigator. Outside MRI scans should be submitted to PACS, and reports submitted to medical records, as soon as possible.

